 - 2) Secondary analysis individuals who were not vaccinated with any vaccine on the index date but had at least one vaccination record in the year prior to the index date (ie, contemporaneous unvaccinated control cohort)
- An self-controlled risk interval (SCRI) design, which will serve as the secondary study design, will be used to compare the incidence of atrial fibrillation and supraventricular arrhythmia during the post-vaccination risk window (eg, 0-3 days following vaccination) to the post-vaccination control window (eg, 4-10 days following vaccination) among ABRYSVO vaccinated individuals.
- Medical records review will be conducted as a separate component to validate/adjudicate cases of atrial fibrillation among ABRYSVO vaccinated individuals within the VHA system.

Population: The study population will consist of individuals with a record of at least one dose of ABRYSVO who are at least 18 years of age on the date of vaccination (ie, index date). Individuals who receive an RSV vaccine from a manufacturer other than Pfizer will be excluded from the study. Contemporary vaccinated controls will be included if they have no record of RSV vaccine and have a record for another vaccine (eg, influenza vaccine, COVID-19 vaccine, and other pre-specified vaccines such as shingles, hepatitis B) within 30 days of a corresponding ABRYSVO vaccinee's vaccination date; the control's index date will be the date of the control's non-RSV vaccine and they will be required to be at least 18 years of age on the index date. Contemporary unvaccinated controls will be included if they have no

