As a secondary analysis, individuals who received ABRYSVO will be compared to individuals not receiving any vaccinations at that point in time but had at least one vaccination record in the year prior to the index date (ie, contemporary unvaccinated controls). The unvaccinated controls will be assigned an index date matched to a corresponding ABRYSVO vaccinee's vaccination date; these individuals can later receive ABRYSVO and enter the vaccination group if all eligibility criteria are met. To address possible selection bias due to health seeking behaviors, the unvaccinated controls will be randomly selected from a population of patients who have regular use of preventive medical care within the VHA system, defined as at least one vaccination record in the year prior to the index date. The index date for the contemporary unvaccinated controls will be selected based on the observed index dates in the vaccinated cohort. If ABRYSVO vaccination is associated with a regular healthcare encounter, the contemporary unvaccinated control will be required to have an encounter within 30 days of the assigned index date, and the date of encounter will be set as the index date to ensure comparability of covariate measurement.

In the primary analysis, the ABRYSVO vaccinated, contemporary vaccinated control, and contemporary unvaccinated control cohorts will be followed for up to 34 days post-index (ie, 0-3 day risk interval plus 30-day diagnosis confirmation window) to assess and confirm the occurrence of atrial fibrillation and supraventricular arrhythmia. In secondary analyses, the cohorts will be followed up to 32 days post-index (ie, 0-1 day risk interval plus 30-day diagnosis confirmation window) and up to 61 days post-index (ie, 0-30 day risk interval plus 30-day diagnosis confirmation window). Individuals will be censored upon the earliest occurrence of disenrollment, death, date of RSV vaccination (for controls who later receive any RSV vaccine only), or end of the risk window. The date of the first atrial fibrillation (or supraventricular arrythmia) case will be considered date of onset.

[figure not shown]

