9.2.1. Inclusion Criteria

Three cohorts will be defined for the main analyses.

- A. A cohort of individuals who received ABRYSVO will form the ABRYSVO cohort and must have:
 - A record for at least one dose of ABRYSVO in the study period from 31 May 2023 (or earliest date of vaccine availability for the indicated population) to 31 May 2026; the date of ABRYSVO vaccination will define the index date for this cohort
 - o No record of an RSV vaccine from a manufacturer other than Pfizer
- B. A cohort of individuals who did not receive ABRYSVO but received another vaccine will form the contemporary vaccinated control cohort and must have:
 - A record for another vaccine (eg, influenza vaccine, COVID-19 vaccine, and other pre-specified vaccines such as shingles, hepatitis B listed in Section 9.3.3) within 30 days of a corresponding ABRYSVO vaccinee's vaccination date; the control's index date will be the date of the control's non-RSV vaccine
 - No record for any RSV vaccine on the index date or in the baseline period (ie, 2 years prior to the index date)
 - Individuals in the vaccinated control cohort who go on to receive an RSV vaccine following their index date will be censored at the time of RSV vaccination. If the RSV vaccine is ABRYSVO, these individuals will contribute to the ABRYSVO cohort starting from the date of ABRYSVO receipt.
- C. A cohort of individuals who did not receive ABRYSVO or another vaccine on the index date but had at least one vaccination record in the year prior to the index date will form the contemporary unvaccinated control cohort and must have:
 - No record for any RSV vaccine on or within 30 days of the index date or in the baseline period (ie, 2 years prior to the index date)

- No record for any other vaccine (eg, those listed in Section 9.3.3) on or within 30 days of the index date
 - This cohort will be assigned an index date matched to a corresponding ABRYSVO vaccinee's vaccination date. If the vaccination is associated with a healthcare encounter (ie, inpatient [IP] or outpatient [OP] visit), the unvaccinated control will be required to have a healthcare encounter within 30 days of the assigned index date, and the date of the healthcare encounter will be set as the index date for the unvaccinated control.

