 - Individuals in the unvaccinated control cohort who go on to receive an RSV vaccine following their index date will be censored at the time of RSV vaccination. If the RSV vaccine is ABRYSVO, these individuals will contribute to the ABRYSVO cohort starting from the date of ABRYSVO receipt.
- o Regular use of preventive medical care, defined as at least one vaccination record between 365 to 31 days prior to the index date.

In addition, individuals in all cohorts must meet the following inclusion criteria to be eligible for the study:

- At least 2 years of continuous enrollment in (ie, no disenrollment from) VHA benefits (ie, the baseline period) prior to the index date
- Complete follow-up (ie, no disenrollment from VHA benefits, death, or receipt of RSV vaccination [for controls who may later receive any RSV vaccine only]) during the risk interval and confirmatory diagnosis window (eg, 34 days of complete follow-up for 0-3 days primary risk interval plus 30-day confirmatory diagnosis window; or 32 days or 61 days for secondary analysis with 0-1 days and 0-30 days risk intervals plus 30-day confirmatory diagnosis window, respectively).

Based on age on the index date, eligible individuals will be further classified into the following two age groups with the following additional inclusion criteria:

- 18-59 years old age group
 - o 18-59 years of age on the index date
 - o For individuals in cohorts B and C, a record for specific conditions that increase the risk for severe RSV as defined by the CDC during the baseline period, identified as those with chronic cardiovascular disease, chronic lung or respiratory disease, end-stage renal disease or dependence on hemodialysis or other renal replacement therapy, diabetes mellitus with complications, neurologic or neuromuscular conditions causing impaired airway clearance or respiratory muscle weakness, chronic liver disease, chronic hematologic

conditions, severe obesity, moderate or severe immune compromise, residence in a nursing home, or other chronic medical conditions or risk factors that a health care provider determines would increase the risk for severe disease due to viral respiratory infection (eg, frailty); list of conditions may be updated to align with the most current CDC definition at the time of data analysis¹⁹

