9.9. Strengths and Limitations of the Research Methods

To identify individuals who experienced safety events associated with ABRYSVO, there will be a comparison of individuals vaccinated with ABRYSVO to contemporary vaccinated or unvaccinated controls which yields a more interpretable result than other planned analyses using SCRI (ie, the increased risk of experiencing a specific safety event due to ABRYSVO). The potential for selection bias (ie, confounding by indication, healthy user bias) will be mitigated by comparing baseline demographic and clinical characteristics between those administered ABRYSVO and the vaccinated or unvaccinated controls. Potential confounders can be accounted for in the statistical analysis to achieve balance between cohorts, using methods such as ATT weighting.⁷⁸ Unmeasured confounding may remain, for instance due to lack of information on clinically important covariates such as family history of atrial fibrillation and left ventricular hypertrophy, but will be assessed through sensitivity analysis of a negative control outcome. To further reduce the potential for healthy user bias, unvaccinated controls will be required to have similar healthcare-seeking behaviors as ABRYSVO vaccinees, including at least 2 years of enrollment in and no disenrollment from VHA benefits prior to their matched index date and at least one vaccination record during the one year prior to their matched index date.

In addition, the SCRI method offers some key advantages. The SCRI approach inherently adjusts for within-individual time-stable confounders, such as age, sex, and confounding by indication. While control intervals can be defined both pre- and post- vaccination, the current study will only use a post-vaccination control period because individuals may be more vigilant for the reporting of possible safety events after they receive a vaccine than before vaccination, which may bias the comparison between a post-vaccine risk interval with a pre-vaccine control interval. Specifically, safety events may be more likely to be reported, or care sought for, after vaccination with ABRYSVO than before, which may result in bias against ABRYSVO. The SCRI design is based on several assumptions including that the occurrence of risk of the event in one risk interval is independent of the occurrence in the subsequent or previous interval.

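### Secondary unvaccinated comparison: the prior-vaccination rule binds controls but not ABRYSVO recipients, and the 30-day no-vaccine window has no stated direction

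*Protocol*

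**What the plan says.** Protocol Section 9.2.1 sets two vaccination rules for the contemporary unvaccinated controls (cohort C). The first is "Regular use of preventive medical care, defined as at least one vaccination record between 365 to 31 days prior to the index date". The second is "No record for any other vaccine (eg, those listed in Section 9.3.3) on or within 30 days of the index date".

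The ABRYSVO cohort (cohort A) needs "A record for at least one dose of ABRYSVO in the study period from 31 May 2023" and no RSV vaccine from another manufacturer. The criteria shared by all cohorts are "At least 2 years of continuous enrollment in (ie, no disenrollment from) VHA benefits (ie, the baseline period) prior to the index date" and complete follow-up. Neither asks recipients for an earlier vaccination.

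Section 9.9 gives the purpose of the rule: "To further reduce the potential for healthy user bias, unvaccinated controls will be required to have similar healthcare-seeking behaviors as ABRYSVO vaccinees". Section 9.1.1 gives the role of the comparison: "As a secondary analysis, individuals who received ABRYSVO will be compared to individuals not receiving any vaccinations at that point in time". The Abstract describes the same controls more briefly, as "individuals who were not vaccinated with any vaccine on the index date but had at least one vaccination record in the year prior". Section 9.7.2.2 gives recipients a weight of one and controls PS/(1-PS), so that the estimate refers to ABRYSVO recipients.

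**The concern.** Two arms are alike on a selection criterion only if both must meet it. Here every control has a vaccination 31 to 365 days before index, while a recipient may or may not. An ATT analysis can re-weight controls but cannot supply a kind of control that the criteria have removed. If recipients without a record differ from the others in atrial fibrillation rate, the secondary hazard ratio carries part of the healthy-user bias that the rule was meant to reduce.

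The second issue is the undirected 30-day window. If it runs both ways, whether a person counts as a control at index depends on what happens in the following month. A new arrhythmia in days 0-3 can itself change whether someone is vaccinated in that month.

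**Working it through.** **1. The plan's own figure.** Table 2 (4:1, age 60 and over, background 33.9 per 1,000 person-years, 4-day interval, one-sided alpha 0.05, 80% power) needs 37,444 recipients for an IRR of 2.0 and 116,493 for 1.5. Check: n = (1.645 + 0.842)² × (λ·RR + λ/4) / (λ(RR - 1))², with λ = 0.0339 × 4/365.25 = 0.000371. This gives 37,470 and 116,573, within 0.1%. No stated number is wrong. The protocol gives no figure for the effect of the cohort C vaccination rules.

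**2. The criteria side by side (Section 9.2.1).**

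| Criterion | ABRYSVO cohort | Unvaccinated controls |
|---|---|---|
| Vaccination 31-365 days before index | not required | required |
| No non-RSV vaccine near index | not required; same-day co-administration is a planned subgroup (9.2.3) | required within 30 days, direction not stated |
| Two years of enrollment, complete follow-up | required | required |

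**3. What weighting can do.** Let f be the share of recipients without a record in the look-back; among controls this share is 0 under any weights. The standardized difference is f / √(f(1 - f)/2) = √(2f/(1 - f)). It reaches the 10% limit of Section 9.7.1 at f = 0.01/2.01, about 0.5%. With the indicator in the propensity model, positivity fails; without it, the imbalance stays. If the background rate in recipients without a record is r times that of the rest, and all else is balanced, the hazard ratio is multiplied by 1 + f(r - 1). Neither f nor r is in the documents.

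**4. How f depends on the look-back (assumptions only).** Suppose ABRYSVO is given with this autumn's influenza dose, 85% take a dose each year, last year's dose date is as likely to fall within 365 days as beyond, and other vaccines arrive at 0.5 to 1 a year (Poisson).
- Days 31-365 (335 days): f = (1 - 0.85 × 0.5) × exp(-0.459 to -0.918) = 0.575 × (0.632 to 0.399) = 36% to 23%.
- Two years: f = 0.15 × (1 - 0.5 × 0.85) × exp(-1 to -2) = 0.086 × (0.368 to 0.135) = 3% to 1%.

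Most of the first figure comes from doses just past day 365. Section 9.3.3 assesses immunization history at index or over a two-year baseline, so those recipients do have counterparts on that covariate.

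**5. Recipients to be identified if the rule also binds recipients: N/q**, with q = 1 - f.

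| Assumed q | IRR 2.0 | IRR 1.5 |
|---|---|---|
| 0.9 | 41,605 | 129,437 |
| 0.7 | 53,492 | 166,419 |
| 0.5 | 74,888 | 232,986 |

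**6. The 30-day window.** For vaccinated controls, Section 9.1.1 writes plus or minus 30 days, and Section 9.2.1 describes that same window simply as within 30 days. The two-sided reading is therefore the protocol's own usage. A person dosed every 365 days is barred on 61 of 365 index dates (17%) if the window is two-sided, and on 31 of 365 (8.5%) if it looks back only.

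If index dates and own doses are spread evenly and independently over an assumed season of L days, the share barred is 1 - (L - 31)(L - 30)/L² two-sided and (31L - 465)/L² looking back:

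| L (days) | Two-sided | Look-back |
|---|---|---|
| 61 | 75% | 38% |
| 92 | 55% | 28% |
| 122 | 44% | 22% |
| 182 | 31% | 16% |

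The gap between the columns is exclusion on future vaccination. If v1 and v0 are the shares vaccinated in days 1-30 among controls with and without an event, the control risk is multiplied by about (1 - v1)/(1 - v0). If an event defers vaccination, v1 is below v0, the control risk is inflated and the hazard ratio is lowered. The documents give neither share.

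**The case against.** The best defence is that every recipient has a vaccination record at index, so asking controls for a recent one is a reasonable analogue. Section 9.9 says the rule reduces bias further, not that it removes it. ATT weighting, the encounter requirement for controls and a negative control outcome (Section 9.7.4.1) also help. No link between dose timing and four-day atrial fibrillation incidence is shown. Restricting recipients narrows a population that Section 9.9 says was kept broad. All of this is fair and limits the weight of the point. None of it makes the rule apply to both arms, or gives the 30-day window a direction.

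A reader might go further in three ways that the documents do not support.

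- *That about half of recipients can have no counterpart.* This needs yearly influenza vaccine only, co-administration, and a covariate cut at 365 days. The rule accepts any vaccination record, and the listed covariate covers two years.
- *That typical autumn vaccinees are shut out as controls.* Anyone dosed more than 30 days before index qualifies through that same-season dose. Some exclusion near a dose is what an unvaccinated control means, and the share in step 6 runs from 16% to 75% with the assumed season and direction.
- *That the Abstract contradicts Section 9.2.1.* The heading of cohort C also speaks only of the index date before its bullets add the 30 days. The Abstract is a summary; aligning it is housekeeping.

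**Conclusion.** The point holds in a limited form. From the text alone, the 31-365 day rule is one-sided, so the criteria do not secure the similarity claimed in Section 9.9, and recipients with no record in the look-back have no like control. Also from the text, the 30-day rule lacks a direction; the protocol's usage elsewhere points to both sides, which selects controls, and only controls, on vaccines received after index.

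The size is unknown. It rests on a vaccination calendar and a prior-vaccination share that the documents do not give, and with two-year immunization history the share without counterparts may be small. No direction of bias is shown for the first issue; the downward direction for the second depends on events deferring vaccination. Only the secondary unvaccinated comparison is touched. The changes are worth making because they are cheap, not because a large bias has been shown.

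**What to change.** For the unvaccinated comparison only:

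1. Apply the same prior-vaccination criterion to ABRYSVO recipients, as the analysis itself or as a sensitivity analysis, and report how many are dropped. Ideally use one look-back for both arms that covers a full prior season; the existing two-year baseline would serve. The exact length is a preference.
2. Limit the no-other-vaccine rule to days -30 to 0. Censor at any later vaccine, preferably in both arms, rather than excluding on it, and state whether the confirmatory-diagnosis window still runs after such censoring.
3. Align the Abstract and Section 9.1.1 with the revised wording, and soften Section 9.9 if recipients are not restricted.

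The cost is a wording change to Section 9.2.1 and reprogramming of one selection step. With restriction, the secondary estimate applies to recipients with a prior vaccination record and the number to be identified rises to N/q; that is modest at q = 0.9 but double at q = 0.5, which is a reason to use the longer look-back. The primary vaccinated-control and SCRI analyses do not change.

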record of any vaccine on the index date but had at least one vaccination record in the year prior to the index date; they will be assigned an index date matched to a corresponding ABRYSVO vaccinee's vaccination date and will be required to be at least 18 years of age on the matched index date. All individuals must be enrolled in (ie, not disenrolled from) VHA benefits during the 2 years prior to the index date (ie, baseline period) and have complete follow-up (ie, no disenrollment from VHA benefits, death, or receipt of RSV vaccination [for controls who may later receive any RSV vaccine only]) during the risk interval and confirmatory diagnosis window. Eligible individuals will be further classified into either the 18-59 years old age group or 60 years and older age group based on their age on the index date; contemporary vaccinated or unvaccinated controls in the 18-59 years old age group are further required to have a record for specific conditions that increase the risk for severe RSV as defined by the Centers for Disease Prevention and Control (CDC) during the baseline period (see "Subgroups" below for specific conditions).

Variables:

- Exposure: Administration of ABRYSVO will be identified based on the following:
 - o Current Procedural Terminology (CPT) code 90678, OR
 - 10 and 11-digit National Drug Codes (NDC) 0069-0207-01, 0069-0250-01, 0069-0344-01, 0069-0344-05, 0069-0344-10, 0069-0651-01, 0069-1265-10, 0069-1265-20, 0069-2465-19, 0069-2465-01, 0069-2465-10; OR
 - o Immunization records that contain data on vaccine code descriptor, vaccine manufacturer (ie, Pfizer), lot number, injection site, and date(s) of immunization.

Relevant codes will be reviewed and amended if new codes are added.

• Outcomes: The study's primary outcome, new onset atrial fibrillation, will be identified by a diagnosis code for atrial fibrillation in any setting during the 0-3 day risk interval for the primary analysis (or 0-1 day or 0-30 day risk interval for secondary analysis), or day 4-10 post vaccination control interval, followed by a confirmatory diagnosis within 30 days after the initial diagnosis and no diagnosis for atrial fibrillation or other supraventricular arrhythmia in the 2 years prior to the index date (ie, "clean window," to rule out pre-existing events). 8,9

The secondary outcome of the study will be new onset supraventricular arrhythmia, including atrial fibrillation, and will be identified in the same manner as the primary outcome.

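### Complete follow-up is an entry condition, but the same events are also censoring events; the entry rule drops AF cases who die in the window and selects controls on post-index RSV vaccination

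*Protocol*

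**What the plan says.** Two rules in the current protocol deal with the same three events.

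- **Entry rule.** Section 9.2.1, in the criteria common to all cohorts, requires "Complete follow-up (ie, no disenrollment from VHA benefits, death, or receipt of RSV vaccination" (RSV vaccination for controls only). The primary analysis calls for "34 days of complete follow-up for 0-3 days primary risk interval plus 30-day confirmatory diagnosis window". The secondary analyses need 32 and 61 days, built the same way from their own risk intervals. The Abstract (section 4) repeats the requirement: individuals must "have complete follow-up (ie, no disenrollment from VHA benefits, death, or receipt of RSV vaccination".
- **Censoring rule.** Section 9.1.1 states: "Individuals will be censored upon the earliest occurrence of disenrollment, death, date of RSV vaccination" (controls only for the last), or end of the risk window. Section 9.2.1 says it again for cohort B, whose members if they later "receive an RSV vaccine following their index date will be censored at the time of RSV vaccination". A matching sentence covers cohort C.

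Two further provisions matter. Controls who later receive ABRYSVO may enter the ABRYSVO cohort (sections 9.1.1 and 9.2.1). Cohort C must also have "No record for any RSV vaccine on or within 30 days of the index date", and a parallel condition covers other vaccines; neither says whether the 30 days run before index, after it, or both.

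**The concern.** Programmers working from section 9.1.1 and from the common criteria in section 9.2.1 would build different cohorts. One keeps a person up to death, disenrollment or RSV vaccination; the other deletes that person altogether. This is not detail deferred to the SAP, because the protocol fixes both rules.

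The entry rule also makes eligibility depend on what happens after the outcome. A vaccinee with confirmed AF on day 1 who dies on day 20 leaves both numerator and denominator. The primary objective (section 8) is the incidence of AF after ABRYSVO, computed as events over observation time (section 9.7.2.1), and the cases lost are among the most severe.

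For controls there is an extra, one-sided condition on the future. An event-free control who takes ABRYSVO on day 14 is deleted as a control but may join the ABRYSVO cohort. A control with AF on day 2 who does the same is deleted as a control and then barred from the ABRYSVO cohort by the baseline AF exclusion in section 9.2.2. That event is counted nowhere.

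**Working it through.** **1. The windows reproduce.**

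| Risk interval | Risk days + 30 | Required follow-up | Risk window ends | Required days after it |
|---|---|---|---|---|
| 0-3 (primary) | 4 + 30 | 34 (days 0-33) | day 3 | 30 of 34 |
| 0-1 | 2 + 30 | 32 (days 0-31) | day 1 | 30 of 32 |
| 0-30 | 31 + 30 | 61 (days 0-60) | day 30 | 30 of 61 |

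**2. The two rules side by side.** Censoring can act only up to the end of the risk window. Anyone who dies, disenrolls or (controls) is RSV-vaccinated by then also does so inside the required follow-up and is already ineligible. Those three triggers are therefore empty in all three analyses. Only the fourth, end of the risk window, still works.

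**3. Expected cases.** Inputs are from section 9.5.1 and Table 2 (60 years and older): 33.9 per 1,000 person-years, 4-day interval, 4:1 matching, IRR 2.0, one-sided 0.05, 80% power.

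- λ = 0.0339 × 4/365.25 = 3.713 × 10⁻⁴ per person.
- Check on Table 2: n = (1.645 + 0.842)² × (2λ + λ/4)/λ² ≈ 37,470, against 37,444 stated. No sample-size figure is in dispute.
- Expected vaccinee cases: 37,444 × 2λ = 27.8.

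**4. Deaths.** The documents give no mortality after AF, so the shares are assumed. If 2%, 5% or 10% of the 27.8 cases die in the window, 0.6, 1.4 or 2.8 are removed. Let f1 and f0 be the shares of vaccinee and control cases who die, with mortality among event-free people alike in both cohorts. The ratio then reads 2.0 × (1 − f1)/(1 − f0):

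- f1 = f0: 2.00, no bias.
- 10% v 5%: 2.0 × 0.90/0.95 = 1.89.
- 20% v 5%: 2.0 × 0.80/0.95 = 1.68.

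**5. Later RSV vaccination of controls.** The documents give no uptake figure either. Let q be the share of event-free controls RSV-vaccinated in the window, and r the uptake among AF cases relative to that. The retained control risk is multiplied by (1 − rq)/(1 − q).

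| q (assumed) | r = 1 | r = 0.5 | True 2.0 reads at r = 0.5 |
|---|---|---|---|
| 5% | 1.000 | 0.975/0.95 = 1.026 | 1.95 |
| 10% | 1.000 | 0.95/0.90 = 1.056 | 1.89 |
| 20% | 1.000 | 0.90/0.80 = 1.125 | 1.78 |

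For r > 1 the factor falls below 1 and the ratio is pushed up.

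**6. Power.** A Poisson-regression approximation is Φ{[ln(IRR)√(Nλ) − 1.645√V0]/√V1}, with N = 5 × 37,444, V0 = 1/(0.2 × 0.8) and V1 = 1/0.8 + 1/(0.2 × IRR). It gives about 81% at 2.0 and about 73% at 1.89.

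**The case against.** The criterion has a rationale. The amendment log shows it was added deliberately in version 2.0. For the parallel enrollment requirement in the SCRI analysis, section 9.1.2 explains that everyone should have the same chance of a confirmed diagnosis and that so short a period should cause little selection bias. One can also call the overlap mere redundancy, with the stricter rule governing. The rationale is fair, but it is given for the SCRI design and for enrollment only. It does not address death or the controls-only vaccination condition. If the stricter rule does govern, the selection on the future follows in full.

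Several stronger readings are tempting and are not supported:

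- *Every fatal AF case is deleted.* Only deaths inside 34 (32 or 61) days are removed. AF on day 2, a second code on day 5 and death on day 40 is counted in the primary analysis.
- *Nobody is ever censored.* End of the risk window still operates.
- *The hazard ratio is biased toward hiding harm.* This needs AF to lower later RSV uptake, or case fatality to be higher among vaccinees. The protocol supports neither. A new cardiac diagnosis could bring more contacts and more vaccination, since section 9.2.1 lists chronic cardiovascular disease as a risk condition for severe RSV.
- *Deleting the criterion recovers all early deaths.* Section 9.3.2 requires a second code within 30 days, so a case who dies before it is lost either way.

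For cohort C, if the 30 days also run forward, the common criterion adds only days 31-33 to the RSV bar in the primary analysis. The text does not settle that reading. For RSV vaccine a look-back is already covered by the 2-year baseline clause, which favours a forward meaning. For other vaccines, the prior-vaccination window of 365 to 31 days before index fits a look-back.

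**Conclusion.** The contradiction stands on the text alone: the same three events cannot both bar entry and be censored, and the sections must be reconciled. Selection on post-index events also stands. Under the entry rule every AF case who dies within the 34-day (32- or 61-day) window leaves the primary incidence estimate, and controls alone are conditioned on no RSV vaccination after index. Equal case fatality would protect the ratio but would not restore those cases to the incidence.

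The effect on the hazard ratio is not fixed by the documents. It is nil if deaths are alike across cohorts and RSV uptake is unrelated to AF. It is a control-rate inflation of about 1.03 to 1.13 if AF halves uptake and 5% to 20% of controls are vaccinated in the window, and it is in the opposite direction if AF raises uptake. These are illustrations on assumed inputs. The case for changing the text rests on the undefined analysis population, not on a predicted bias.

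**What to change.** For the cohort analyses:

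1. Determine eligibility from information up to the index date, and delete the complete-follow-up criterion from section 9.2.1 and the Abstract.
2. Keep the section 9.1.1 censoring, applied within the risk interval.
3. Let the 30-day confirmation window run regardless of later RSV vaccination, so that a control with a first AF code before vaccination can still be confirmed.
4. Add a sensitivity analysis that counts a first AF code followed by death before a second code as a case. The main outcome definition is unchanged.
5. For cohort C, state that the 30-day vaccine condition means on or before index, and handle later vaccination by censoring.

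The cost is protocol and SAP wording. A few cases will have an incomplete confirmation window because of death or disenrollment; the sensitivity analysis shows the effect of the deaths. The Table 2 sample sizes do not change.
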